11.9.2 Other Efficacy Endpoints

- **Progression Free Survival (PFS):** Defined as the time from the date of the first dose of study drug until the date of progressive disease or death from any cause, whichever occurs first. PFS will be censored as follows:
 - Patients who had no event (i.e., they did not die or have PD) will be censored at the date of their last tumor assessment.
 - Patients with no baseline assessment will be censored at the date of the first dose.
 - Patients who started a new anti-cancer therapy prior to documented PD or death will be censored at the last tumor assessment prior to initiation of new anti-cancer therapy.
- **Duration of Response (DOR):** Defined as the time from the date of first documented response (CR or PR) until the date of progressive disease or death from any cause, whichever occurs first, after achieving response. DOR will be censored as follows:
 - Patients who had no event (i.e., they did not die or have PD) will be censored at the date of their last tumor assessment.
 - Patients who started a new anti-cancer therapy prior to documented PD or death will be censored at the last tumor assessment prior to initiation of new anti-cancer therapy.
- **Duration of Stable Disease (DSD):** Defined as the time from the date of first documented Stable Disease (SD) response until the date of progressive disease or death from any cause, whichever occurs first, after achieving SD response. DSD will be censored as follows:
 - Patients who had no event (i.e., they did not die or have PD) will be censored at the date of their last tumor assessment.
 - Patients who started a new anti-cancer therapy prior to documented PD or death will be censored at the last tumor assessment prior to initiation of new anti-cancer therapy.
- **Disease Control Rate (DCR):** Defined as the percentage of patients who have achieved CR, PR, or SD lasting at least 6 months.
- **Duration of Disease Control (DDC):** Defined as the time from the date of first documented response (CR or PR) or Stable Disease (SD) until the date of progressive disease or death from any cause, whichever occurs first, for patients with CR, PR or SD lasting at least 6 months. DDC will be censored as follows:
 - Patients who had no event (i.e., they did not die or have PD) will be censored at the date of their last tumor assessment.

- Patients who started a new anti-cancer therapy prior to documented PD or death will be censored at the last tumor assessment prior to initiation of new anti-cancer therapy.
- **Rate of patients with CR+PR+SD (regardless of duration):** Defined as the percentage of patients who have achieved CR, PR, or SD.
- **Duration of CR+PR+SD:** Defined as the time from the date of first documented response (CR or PR) or Stable Disease (SD) until the date of progressive disease or death from any cause, whichever occurs first, for patients with CR, PR or SD. The duration will be censored as follows:
 - Patients who had no event (i.e., they did not die or have PD) will be censored at the date of their last tumor assessment.
 - Patients who started a new anti-cancer therapy prior to documented PD or death will be censored at the last tumor assessment prior to initiation of new anti-cancer therapy.

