3.3. Confirmatory Measurement/Duration of Response

3.3.1. Confirmation. The main goal of confirmation of objective response in clinical trials is to avoid overestimating the response rate observed. This aspect of response evaluation is particularly important in nonrandomized trials where response is the primary endpoint. In this setting, to be assigned a status of partial response or complete response, changes in tumor measurements must be confirmed by repeat assessments that should be performed no less than 4 weeks after the criteria for response are first met.

In the case of stable disease, measurements must have met the stable disease criteria at least once after study entry at a minimum interval of 8 weeks.

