APPENDIX C

COMPOSITE TUMOR RESPONSE CRITERIA FOR PATIENTS WITH LOCALLY ADVANCED BASAL CELL CARCINOMA

For all patients with locally advanced basal cell carcinoma (BCC), externally visible target lesions will be chosen by the investigator *and* must include any lesions that are both externally visible and measurable according to the Response Evaluation Criteria in Solid Tumors (RECIST). The externally visible component of all target lesions should be at least 10 mm in the longest dimension, to facilitate accurate and reproducible measurement. Standardized digital photographs of the externally visible component of all target lesions must be obtained at baseline and at the time of each tumor assessment (see Appendix H). For patients with a target lesion that contains both an externally visible and a RECISTmeasurable component, appropriate imaging studies (computed tomography or magnetic resonance imaging) will be used to assess the RECIST component of tumor response (see Appendix B). Investigators must also provide a clinical description of the target lesion(s) at baseline and at each tumor assessment, as well as comments on any changes in the lesion(s) since the previous assessment.

All patients will undergo baseline and on-study biopsies of target lesions per Appendix G; in patients achieving a clinical response, histologic analysis of on-study biopsies will be used for final determination of complete versus partial response (see below).

Clinical Response Criteria (for all patients with locally advanced BCC)

A. Externally Visible Tumor Dimension

The externally visible component of target lesion(s) will be measured in the longest dimension at each tumor assessment and will be documented using standardized digital photography. If the border of the tumor is no longer visible but a scar is present, the dimensions of the scar should be measured.

Response criteria for tumor dimension are as follows:

- Complete Response (CR): *all* target lesion(s) no longer visible, maintained for at least 4 weeks
- Partial Response (PR): decrease of 30% or greater in the sum of the longest dimension of target lesion(s), maintained for at least 4 weeks
- Stable Disease (SD): not meeting criteria for CR, PR, or progressive disease (PD)
- Progressive Disease (PD): increase of ≥ 20% in the sum of the longest dimension of target lesion(s)

B. Tumor Ulceration (only for patients whose target lesion[s] are ulcerated at baseline)

Response criteria are as follows:

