11.9.1 Primary Efficacy Endpoints

The efficacy endpoints include the following:

• **Best Overall Response**: Assessed separately for patients with mBCC and with locally advanced BCC as a function of radiographic, photographic, and pathologic review (Appendices B, C, G and H of the protocol) as described below.

For patients with mBCC: Overall Response will be assessed using the Response Evaluation Criteria in Solid Tumors (RECIST).

For patients with locally advanced BCC: Overall response will be assessed using a composite response endpoint that incorporates externally visible tumor dimension and tumor ulceration, as well as RECIST for lesions with a RECIST-measurable component.

Patients will be categorized as Complete Response (CR), Partial Response (PR), Stable Disease (SD), Progressive Disease (PD), and Not Evaluable (NE) in Overall Response at each assessment.

• **Objective Response**: Defined as a Complete Response (CR) or Partial Response (PR) in Overall Response determined on two consecutive assessments ≥ 4 weeks apart.

In patients with locally advanced BCC achieving a CR or PR, tumor biopsies will be used in the final determination of CR. CR is defined as absence of residual BCC on biopsy; PR is defined as presence of residual BCC on biopsy.

• Analysis of the changes in *Gli1* expression will be conducted by the OncoCyte Corporation (formerly Insight Genetics) and a separate report will be prepared. Thus detailed analysis is not included in this SAP.

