11.10 Efficacy Analyses

11.10.1Primary Efficacy Analyses

The primary endpoints will be assessed in the Efficacy population, overall and separately for patients with mBCC and patients with locally advanced BCC.

The objective response rate (ORR) will be calculated as the number of patients satisfying the OR criteria divided by the number of subjects in the Efficacy population. Patients without at least one post-baseline response assessment will be treated as non-responders. Further, patients who experience progressive disease but continue treatment under the protocol and experience partial or complete response in a subsequent tumor assessment, will be considered partial or complete responders. A continuity-corrected 95% confidence interval based on the normal approximation will accompany each ORR.

Complete response rates (CRR) will be summarized in parallel fashion to ORR.

11.10.20ther Efficacy Analyses

PFS will be analyzed using the Kaplan-Meier method in the Efficacy population, separately for patients with mBCC and patients with locally advanced BCC.

Summary statistics from the Kaplan-Meier distribution will be determined, including the median and estimates at 3, 6, 9, 12 months. These statistics will be provided as point estimates with 95% confidence intervals.

DOR summary will include at least median (in months), range and patients (n, %) with observed DOR for at least 6 months.

DSD summary will include at least median, range, min, max and patients (n, %) with observed SD for at least 6 months.

DCR summary will include at least median, range, min, max and patients (n, %) with observed DCR for at least 6 months.

Summary of patients with CR+PR+SD (regardless of duration) will include at least median, range, min, max and patients (n, %) with observed CR+PR+SD.

11.10.3Subgroup Analyses

Not applicable.

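### SAP 11.9.2 does not tie duration of response to confirmed responders and can censor PFS before first dose, so two descriptive endpoints can hold inconsistent or invalid records

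*SAP*

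**What the plan says.** **DOR.** SAP 11.9.1 classifies each patient as CR, PR, SD, PD or "Not Evaluable (NE) in Overall Response at each assessment". It then defines Objective Response as a CR or PR "determined on two consecutive assessments ≥ 4 weeks apart", and 11.10.1 uses that definition for the ORR numerator. SAP 11.9.2 defines DOR separately: "Defined as the time from the date of first documented response (CR or PR) until the date of progressive disease or death". That definition neither refers to Objective Response nor asks for confirmation. SAP 11.10.2 asks for the median, the range and the number and percentage at 6 months or more, without naming the denominator.

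Three protocol texts bear on what CR and PR mean:
- Appendix B, 3.3.1 (used for mBCC): "to be assigned a status of partial response or complete response, changes in tumor measurements must be confirmed by repeat assessments".
- Appendix C (locally advanced BCC), PR by visible dimension: "decrease of 30% or greater in the sum of the longest dimension of target lesion(s), maintained for at least 4 weeks". CR by dimension and CR by ulceration carry the same 4-week condition.
- Appendix C, closing paragraph: a PR is also given when all previously inoperable target lesions become operable and surgery achieves clear margins. No second assessment is required.

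**PFS.** The clock starts at first dose. SAP 11.9.2 has three censoring bullets:
- The general rule reads: "Patients who had no event (i.e., they did not die or have PD) will be censored at the date of their last tumor assessment".
- The fallback to first dose covers a missing baseline only: "Patients with no baseline assessment will be censored at the date of the first dose".
- The new-therapy rule sends anyone who begins another anti-cancer treatment before PD or death back to the last assessment before that treatment.

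Protocol 12.1(e) places baseline imaging in the 14 days before Day 1, and later assessments every 8 weeks and at study completion or early termination. For ORR, SAP 11.10.1 foresees patients with nothing after baseline: "Patients without at least one post-baseline response assessment will be treated as non-responders". PFS has no matching rule.

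**The concern.** DOR is normally read as describing the responders counted in the ORR. If its set is built from any visit-level CR or PR, it can contain patients whom the ORR counts as non-responders, and short unconfirmed responses would lower the median and the share lasting 6 months. With 10 patients planned per expansion cohort, and only 2 mBCC patients enrolled in that part (SAP 6), one patient can change the summary visibly.

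For PFS, the last tumour assessment of a patient never scanned on study is the baseline scan, which precedes time zero. The rule then gives a negative time. The one first-dose fallback addresses a missing baseline instead, and unlike the first bullet it is not limited to patients without an event. Taken literally, it would censor a patient who died. These are faults in the stated rules, which someone would have to repair during programming.

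**Working it through.** **The plan's own figure.** The plan gives no number for DOR or PFS. Its one design figure that can be recomputed, the 80% interval for 2 responses in 10 (SAP 6), reproduces as an exact Clopper-Pearson interval: 5.45% to 44.96%, against the stated 5.5% to 45.0%. Nothing below depends on it.

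**Step 1: can a patient enter DOR without being an ORR responder?** There are two routes.
- *Visit-level labels.* SAP 11.9.1 labels CR or PR at each assessment and adds confirmation only when defining Objective Response. Protocol 12.1(e) also times confirmation from the initial documentation of response, so documentation comes first. A patient with PR at Week 8 whose 4-week repeat is missed or not a response, and who has PD at Week 16, has a documented PR but no Objective Response.
- *Surgical PR.* The closing paragraph of Appendix C gives a PR that need not be seen at two assessments.

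**Step 2: size for DOR (assumed data).** Take two confirmed responders with DOR of 8 and 10 months in a cohort of 10. Each unconfirmed responder progresses at the next 8-week visit: 56 / 30.4375 = 1.84 months. Plain medians, all durations observed:

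| Unconfirmed added | DOR n | Median (months) | Share ≥ 6 months | ORR |
|---|---|---|---|---|
| 0 | 2 | (8 + 10)/2 = 9.0 | 2/2 = 100% | 2/10 |
| 1 | 3 | 8.0 | 2/3 = 67% | 2/10 |
| 2 | 4 | (1.84 + 8)/2 = 4.9 | 2/4 = 50% | 2/10 |
| 3 | 5 | 1.8 | 2/5 = 40% | 2/10 |

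**Step 3: PFS time for a baseline-only patient.** Time = censoring date − first-dose date. With the scan on Day −14 to Day −1, this is −14 to −1 days (−13 to 0 if one day is added). The result is the same for a patient who starts new therapy before any on-study scan, because the last assessment before that therapy is also the baseline scan.

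**Step 4: effect on the PFS curve (assumed data).** Eight followed patients have times 56, 56, 112, 112, 168, 168, 224 and 280 days, with the second 112 and the 224 censored. Add two baseline-only patients, handled three ways:

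| Handling | N | Minimum time | S(56) | S(112) | S(168) | S(280) |
|---|---|---|---|---|---|---|
| Dropped | 8 | 56 | 0.75 | 0.625 | 0.3125 | 0 |
| Censored at first dose | 10 | 0 | 0.75 | 0.625 | 0.3125 | 0 |
| Left negative | 10 | −14 | 0.75 | 0.625 | 0.3125 | 0 |

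The curve is identical. N, the number censored and the range are not.

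**Step 5: a lost death does move the curve.** To the same eight, add one patient with no baseline assessment who dies before day 56. Counted as an event: S = 8/9 = 0.889 at the death, then 0.889 × 6/8 = 0.667 at day 56. Censored at first dose under the second bullet: S(56) = 0.75. Such a patient can be in the PFS set, because the Efficacy population (SAP 7) requires a baseline biopsy consistent with BCC, not a baseline scan.

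**The case against.** **DOR.** SAP 11.9.1 says response is assessed under the protocol appendices, and Appendices B and C attach confirmation or 4-week maintenance to CR and PR. The flowchart footnotes in Appendix A also call for a repeat scan after 4 weeks. On that reading an unmaintained decrease is not a PR and starts no DOR, and the first documented response is simply the start of a confirmed one. This is a reasonable reading, and it narrows the problem. It does not remove it: the SAP does not state it for DOR, it sits awkwardly with labels given at each assessment, and it does not cover the surgical PR.

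A reader might infer that DOR definitely starts at any CR or PR. The documents do not support that; they leave two readings open. Nor is dating DOR from first documentation a fault in itself.

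**PFS.** A patient who stops before Week 8 is still due an assessment at early termination (protocol 12.1(e)), with the return visit within 30 days of last dose (protocol 12.4). Only those who also miss that assessment, or who start new therapy before any on-study scan, are affected. A treated patient with no baseline assessment should be rare, since baseline imaging is mandatory. Both points stand and make the affected group small.

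A reader might also infer that negative times would be dropped or would distort the curve. The documents do not say how they would be handled, and Step 4 shows no change in the curve either way. SAP 10.1 lists derived variables by subject, so an odd record would at least be visible.

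**Conclusion.** The point holds as a fault in the rules, not as a demonstrated fault in the data. As written, SAP 11.9.2 can put patients in DOR who are outside the ORR numerator, and can give PFS times 1 to 14 days before time zero or override a death. The PFS part is the firmer of the two, because no other text closes it. The DOR part is an ambiguity that the appendices narrow but do not settle.

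DOR n, median and share at 6 months or more can change. For PFS, N, the number censored and the range can change, and the Kaplan-Meier estimates change only if a death is lost. Both are descriptive endpoints with no formal testing (SAP 10.5), and the RP2D and ORR are untouched. The correction should be made, but nothing central to the trial turns on it.

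The DOR and Kaplan-Meier figures rest on invented patients and show direction and scale only. The 14-day bound assumes that the baseline window in protocol 12.1(e) is kept. It would be wrong to infer that the trial's datasets do contain such records: the documents do not show whether any patient meets these conditions.

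**What to change.** **DOR.** In SAP 11.9.2, restrict DOR to patients who meet Objective Response in 11.9.1, dated from the first of the two qualifying assessments. State whether a surgical PR under protocol Appendix C counts, and apply the same answer to ORR and DOR. Name the denominator for the 6-month percentage.

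**PFS.** Replace the censoring bullets so that:
- a patient with no post-baseline tumour assessment, or none before new anti-cancer therapy, and no prior death is censored at first dose;
- a death before new anti-cancer therapy is an event whether or not a baseline scan exists;
- other event-free patients are censored at the last post-baseline assessment, or the last one before new therapy.

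**Cost.** A few sentences in the SAP and matching programming specifications; no new data. The one real decision is the surgical PR. The SAP already records early termination of mBCC enrolment, so the change should be dated relative to data review and reported as SAP 1 requires for deviations from the plan.

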3.2. Response Criteria

3.2.1. Evaluation of target lesions. This section provides the definitions of the criteria used to determine objective tumor response for target lesions. The criteria have been adapted from the original WHO Handbook, taking into account the measurement of the longest diameter only for all target lesions:

Complete Response—the disappearance of all target lesions; Partial Response at least a 30% decrease in the sum of the longest diameter of target lesions, taking as reference the baseline sum longest diameter; Progressive Disease—at least a 20% increase in the sum of the longest diameter of target lesions, taking as reference the smallest sum longest diameter recorded since the treatment started or the appearance of one or more new lesions; Stable Disease—neither sufficient shrinkage to qualify for partial response nor sufficient increase to qualify for progressive disease, taking as reference the smallest sum longest diameter since the treatment started. If the investigator's assessment of progressive disease is equivocal, and in the investigator's opinion the patient is still deriving benefit from treatment, treatment with CX-4945 should be continued, and the patient should be re-evaluated at the next tumor assessment timepoint.

3.2.2. Evaluation of nontarget lesions. This section provides the definitions of the criteria used to determine the objective tumor response for nontarget lesions: complete response—the disappearance of all nontarget lesions; incomplete response/stable disease—the persistence of one or more nontarget lesion(s); and progressive disease—the appearance of one or more new radiographically identified lesions and/or unequivocal progression of existing nontarget lesions. A new radiographically identified lesion is defined as a lesion that has not previously been seen in prior imaging studies, and that has increased in size to either a diameter larger than the size of the slice thickness being used for that imaging modality or at least 5 mm, whichever is larger.

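### DSD in SAP 11.9.2 counts later response time as stable disease and, for SD under RECIST, leaves out roughly the first 8 weeks from first dose

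*SAP*

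**What the plan says.** SAP 11.9.2 sets out several time-based endpoints side by side.

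- PFS is the "time from the date of the first dose of study drug until the date of progressive disease" or death.
- DSD is "Defined as the time from the date of first documented Stable Disease (SD) response until the date of progressive disease" or death. Its two censoring rules cover patients without an event and patients who start new anti-cancer therapy. Neither mentions a later CR or PR.
- Duration of disease control (DDC) and duration of CR+PR+SD share one opening: "Defined as the time from the date of first documented response (CR or PR) or Stable Disease (SD) until the date of progressive disease". DDC is limited to a subset: "for patients with CR, PR or SD lasting at least 6 months".
- Disease control rate (DCR) is the "percentage of patients who have achieved CR, PR, or SD lasting at least 6 months". No start date is given.

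SAP 11.10.2 then asks for a 6-month share: "DSD summary will include at least median, range, min, max and patients (n, %) with observed SD for at least 6 months". It gives no day-to-month conversion and no denominator.

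In the protocol, tumor assessments are every 8 weeks (section 12.1, item e) within 3 days either side (section 12.3). Appendix B, section 3.2.1, judges stable disease "taking as reference the smallest sum longest diameter since the treatment started". The protocol defines none of the durations above.

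**The concern.** Two features of the DSD clock pull in opposite directions.

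First, it runs on through a response. A patient seen once with SD, who then responds, keeps accumulating DSD until progression. The table would label that time stable disease, and the same days would appear again under duration of response (DOR).

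Second, it starts late. Under RECIST, an SD reading at the week 8 scan compares that scan with the smallest sum since treatment began, so it already describes weeks 0 to 8. Starting at the scan date drops those weeks. First documentation is a natural start for DOR, because response is a new event. SD is the absence of sufficient change since treatment began.

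At stake is whether the reported share with SD of at least 6 months means what its label says. That share can include patients who mostly had a response and exclude patients who were progression-free on study for more than 7 months.

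**Working it through.** **Inputs.** Scheduled scans fall at weeks 8, 16, 24, 32 and 40, that is 7w days after first dose, give or take 3 days (protocol 12.1 and 12.3). Start and end dates are those of SAP 11.9.2. The plan states no figure for DSD, DDC or DCR, so there is none to reproduce. Month length is not given; I assume 28, 30, 30.4375 and 31 days.

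**1. Response counted as SD.** SD at week 8, PR at week 16, PD at week 40:
- DSD = 280 − 56 = 224 days = 224/30.4375 = 7.4 months, so the 6-month cut is passed.
- DOR = 280 − 112 = 168 days = 5.5 months.
- SD before the response: 112 − 56 = 56 days, with one SD scan.

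The 168 days from PR to PD therefore count in both DSD and DOR.

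**2. Late start, nominal schedule.** For SD first documented at week 8, find the earliest PD scan that meets the cut. The first-dose clock needs 7w ≥ 6 months. The SAP clock needs 7w − 56 ≥ 6 months.

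| Month (days) | 6 months (days) | First-dose clock | SAP clock |
|---|---|---|---|
| 28 | 168 | week 24 (168) | week 32 (168) |
| 30 | 180 | week 32 (224) | week 40 (224) |
| 30.4375 | 182.6 | week 32 (224) | week 40 (224) |
| 31 | 186 | week 32 (224) | week 40 (224) |

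Example: SD at week 8 and PD at week 32 gives PFS of 224 days (7.4 months) but DSD of 224 − 56 = 168 days (5.5 months). For an event on any date, such as a death, 6 months of DSD needs 56 + 182.6 = 238.6 days from first dose (7.84 months).

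**3. The same with the 3-day windows.** For 30- to 31-day months (cuts of 180 to 186 days):
- First-dose clock: week 24 gives at most 171 days (fail); week 32 gives at least 221 (pass).
- SAP clock: week 32 gives at most 227 − 53 = 174 days (fail); week 40 gives at least 277 − 59 = 218 (pass).

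The shift is one scan throughout. For 28-day months (cut of 168 days) it is not fixed:
- SD on day 59, scans on days 168 and 224: the first-dose clock passes at week 24. The SAP clock gives 224 − 59 = 165 at week 32 (fail) and passes at week 40. Shift: two scans.
- SD on day 53, scans on days 165 and 224: the first-dose clock fails at week 24 and passes at week 32. The SAP clock gives 224 − 53 = 171 and also passes at week 32. Shift: none.

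**4. Illustration of the late start on the reported share.** The documents give no PFS distribution. Assume exponential PFS, S(t) = 0.5^(t/median), 30.4375-day months, progression found on the scan grid, and all patients as denominator. The share lost to the later start is S(24 weeks) − S(32 weeks):
- median 4 months: 0.384 − 0.279 = 10.5 points
- median 6 months: 0.529 − 0.427 = 10.2 points
- median 12 months: 0.727 − 0.654 = 7.3 points

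If the denominator is patients with SD at week 8, dividing by S(8 weeks) gives 14.4 points (median 4 months) to 8.2 points (median 12 months).

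**The case against.** The best defense is that the SAP clock is explicit, computable and the shorter choice. Appendix B sections 3.2.1, 3.2.3 and 3.3.1 say how to classify a response; none of them sets a duration clock. Time from first dose is already reported through PFS, with Kaplan-Meier estimates at 3, 6, 9 and 12 months, and derived variables are listed by subject. Moving the start lengthens durations in an uncontrolled trial after early termination is known. All of this stands against calling the late start an error. None of it answers the first point: as worded, DSD counts response as stable disease.

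A reader might infer more than the documents support:
- **That the SAP contradicts the protocol.** It does not, because the protocol defines no SD duration.
- **That all three durations discard observed stability.** For a patient whose first scan shows CR or PR, the weeks left out of DDC and duration of CR+PR+SD are time to response. For externally visible lesions, Appendix C gives no reference point for SD, so the RECIST argument covers metastatic disease and the RECIST component of locally advanced disease only.
- **That the shift is always exactly one scan.** That holds for 30- to 31-day months on scheduled scans. It does not hold at 28 days with the visit windows, nor for deaths, early-termination scans, 4-week confirmation scans or 3-monthly follow-up.
- **That DCR is shifted by 8 weeks.** DCR has no stated start, so it carries the shift only if it borrows the DDC clock. The adjacent DDC entry makes that a plausible reading. This is a gap to fill, not a bias shown.

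**Conclusion.** The point holds, at minor severity. The firm part is that DSD as worded reports response time as stable disease: in the example, 168 of 224 days are response, and the patient is counted as having SD for at least 6 months. It rests only on the SAP text and the scan schedule.

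The second part is a weakness of definition. When the first scan shows SD under RECIST, about 8 weeks are left out, and with 30- to 31-day months the 6-month cut moves from the week 32 to the week 40 scan. With 28-day months the move is one scan on the nominal schedule and zero to two within the windows. The loss of roughly 7 to 14 percentage points depends on an assumed exponential PFS and an unstated denominator, so it is illustrative only.

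The endpoints are descriptive. The RP2D decision and ORR do not use these clocks.

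**What to change.** In SAP 11.9.2:

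1. Restrict DSD to patients whose best overall response is SD. Appendix B section 3.2.3 ties best response to confirmation, so say whether a patient with an unconfirmed PR stays in.
2. Measure DSD, and the SD-based part of DDC and of duration of CR+PR+SD, from first dose to PD or death.
3. Keep DOR from first response.
4. Put the change in a dated SAP amendment and show the present first-documented-SD clock beside it. SAP section 6 shows that early termination was already known.

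As clarification in the same edit, apply the same clock to the DCR 6-month condition, and state the month conversion and the denominator of the 6-month shares.

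The cost is wording and a few derived dates, with no new data. The downsides should be disclosed. SD durations lengthen by about 8 weeks and come close to PFS in patients without immediate PD. DCR can only rise or stay the same relative to the DDC clock. Within DDC and duration of CR+PR+SD, a first-scan responder would start about 8 weeks later than a first-scan SD patient with the same progression date, so the two start rules must be stated.
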